### Study Period (Visits 7-15):

The study period begins at Visit 7 and ends at the conclusion of Visit 15.

[figure not shown]
All subjects will use Lyumjev insulin for the remainder of the study. They will continue using the MiniMed 780G system, extended infusion set and extended reservoir. All SmartGuard features will be activated and should be used for the duration of the study period.

Subjects should use the system with SmartGuard turned on, while also using Lyumjev insulin at all times. When prompted by the pump, subjects should take appropriate measures and follow directions on the pump to remain in or return to SmartGuard. During times when subjects are not able to use SmartGuard. they should use the system in Manual Mode (e.g., with Suspend before low or Suspend on low activated).

Therapy at Screening	Pump Setting During Study Period
CSII	SmartGuard with Auto Correction ON
SAP (no closed loop)	SmartGuard with Auto Correction ON
SAP (with closed loop) in non-Medtronic pump	SmartGuard with Auto Correction ON
SAP (with closed loop) in Medtronic pump as Auto Mode	SmartGuard with Auto Correction ON

During the first 3 weeks (between Visits 7 and 11) of the study period, a 120 mg/dL Auto Basal Target should be set. It is recommended that Active Insulin Time is initially set to 4 hours and then titrated towards 2-3 hours at investigator's discretion.

20-DEC-2023 Revision 3.0 Page 8 of 25

During the next 3 weeks (between Visits 11 and 13) of the study period, the Auto Basal Target setting should be set to 100 mg/dL. Active Insulin time is recommended to be set to 2-3 hours or at investigator discretion.

During the remaining weeks of the study (any time after Visit 13) of the study period, the auto basal target as well as Active insulin time should be set to what is best for the individual subject, at investigator discretion.

**Note:** The Auto Basal target setting and Active Insulin Time should be set as recommended above unless there is a documented safety reason that would not permit these settings to be used.

After completion of training on SmartGuard functions, subjects and their parents/caregivers (if applicable) may attend additional visits in the days immediately following the start of SmartGuard use, as needed. They may also take advantage of having access to the digital learning content, provided it is available at study start.

### **Staged Enrollment:**

The enrollment of pediatric subjects 7-17 years of age into the study may not proceed until N=10 subjects 18 years of age or older have completed 30 days of the study period and the Data Monitoring Committee (DMC) has determined it is safe for subjects 7-17 years of age to be enrolled in the study.

### SMBG recommendations for the MiniMed 780G system:

Calibration is not required with the MiniMed™ 780G system using Guardian 4 CGM. However, a calibration is optional and it will automatically occur any time a blood glucose (BG) is entered. Occasionally, subjects may receive a notification if the pump needs a BG to enter or stay in the SmartGuard™. Subjects will be instructed to perform SMBG if their symptoms do not match the sensor glucose (SG) value (i.e., they develop symptoms of hypoglycemia or hyperglycemia, but the SG value does not correlate with their symptoms).

### **Meal and Exercise Challenges:**

Subjects will be asked to participate in meal and exercise challenges during the run-in and study period.

- All challenges are at least 4 hours in duration, beginning at the time when the challenge meals or exercise are started
- There should be no more than one meal challenge on a single day.
- Meal and exercise challenges should not be scheduled on the same day during the specified time periods.

For example: A study period regular sized or large sized meal challenge should not take place on the same day as an exercise challenge

Subjects will be asked to check BG at the start of the meal/exercise, as well as 2 hours and 4 hours after the start of the meal/exercise and provide insulin correction as necessary.

It is important for subjects to avoid additional meal/snack or exercise up to 4 hours after the start of each challenge. If additional meal/snack is consumed or exercise is done within 4 hours after the start of the challenge, the subject will acknowledge this on the challenge log. Content and timing of the meal and

20-DEC-2023 Page 9 of 25 Revision 3.0

exercise, along with answers to challenge questions, will be recorded on a log provided by the study team.

### Meal Challenges for all Subjects (Run-in and Study Period):

The following meal challenges are required during the run-in and study periods:

- Two meal challenges during the run-in period with subjects using the system in **Manual Mode** (SmartGuard must be turned off at least 6 hours prior to the meal challenge for subjects using it during the run-in period) - between Visits 5 and 7
  - One Regular sized meal with *missed meal bolus* at lunch
  - One Large sized meal at breakfast, lunch or dinner
- Two meal challenges during the study period with subjects using the system in SmartGuard, Auto Basal target set at 120 mg/dL - between Visits 9 and 11 of study period
  - One Regular sized meal with *missed meal bolus* at lunch
  - One Large sized meal at breakfast, lunch or dinner
- Two meal challenges during the study period with subjects using the system in SmartGuard, Auto Basal target set at 100 mg/dL - between Visits 12 and 13 of study period
  - One Regular sized meal with *missed meal bolus* at lunch
  - One Large sized meal at breakfast, lunch or dinner
- One meal challenge during the study period with subjects using the system in SmartGuard, Auto Basal target set at investigator's discretion – at any time after Visit 13 of study period
  - One Large sized meal at breakfast, lunch or dinner

Meal challenges should only start if the following conditions are met:

- SMBG at start of meal is < 200 mg/dL
- Sensor glucose is available.

Timing	Settings/Conditions	Meal Size	Meal Type	Notes
Run-in Period between visits 5 and 7	Manual Mode only Missed meal bolus	Regular sized meal	Lunch	Meal content, meal size and time of meal consumption should be established so that regular sized meal challenges during the study period can be matched
Run-in Period between visits 5 and 7	Manual Mode only	Large sized meal	Breakfast Lunch or Dinner	Meal content, meal size and time of meal consumption should be established so that large sized meal challenges during the study period can be matched
Study Period, between Visits 9 and 11	SmartGuard (120 mg/dL setpoint) Missed Meal bolus	Regular sized meal	Lunch	Meal content, meal size and time of meal consumption should match regular meal taken during run-in and the

				regular meal taken at the 100 mg/dL setpoint
Study Period, between Visits 9 and 11	SmartGuard (120 mg/dL setpoint)	Large sized meal	Breakfast, Lunch or Dinner	Meal content, meal size and time of meal consumption should match meal at Setpoint of 100 mg/dL and run-in period meal
Study Period, between Visits 12 and 13	SmartGuard (100 mg/dL setpoint) Missed meal bolus	Regular sized meal	Lunch	Meal content, meal size and time of meal consumption should match regular meal taken during run-in and the regular meal taken at the 120 mg/dL.
Study Period, between Visits 12 and 13	SmartGuard (100 mg/dL setpoint)	Large sized meal	Breakfast Lunch or Dinner	Meal content, meal size and time of meal consumption should match meal at Setpoint of 120 mg/dL and run-in period large sized meal
Study Period Any time after Visit 13	SmartGuard (Auto Basal target at investigator's discretion )	Large sized meal	Breakfast Lunch or Dinner	Meal content, meal size and time of meal consumption should match large meal at Setpoint of 120 mg/dL /100mg/dL and run-in period large sized meals

### **Regular Sized Meal Challenge with Missed Meal Bolus:**

[figure not shown]
Between visits 5 and 7 for the run-in period, while subjects are in Manual Mode with CGM, they will be asked to consume a meal without administration of a Meal Bolus at lunch. The size of the meal should be equivalent to what subjects would normally eat at this mealtime.

During the study period, once at each Auto Basal setpoint (i.e. 120 mg/dL and 100 mg/dL), subjects will be asked to consume the same regular sized lunch meal that they had during the run-in period. For example, if the regular sized meal was consumed without an insulin bolus for the meal at 12 p.m. during the run-in period, that same regular sized meal should be consumed at approximately the same time of day at each setpoint during the study period. Subjects will be asked to check BG at the start of the meal, as well as 2 hours and 4 hours after the start of the meal and take bolus correction as necessary. Details should be recorded, on the log.

### **Large sized Meal Challenges:**

On large sized meal challenge days, subjects will be instructed to eat one meal with at least 50% higher caloric intake, including 50% more carbohydrates and 50% higher in fat. It is recommended that subjects eat food at restaurants or consume prepared meals. The FoodPrint™ app (as well as questions that will be asked by investigational center staff during visits following meal challenges) will be used by subjects to collect information about the food that was eaten, the name of the restaurant (if applicable) and subject confirmation that meal size was at least 50% more in terms of calories, carbohydrates and fat.

20-DEC-2023 Revision 3.0 Page 11 of 25

The timing of the meal challenges will be at the investigator's discretion. The subject's parent/caregiver or companion should be physically present in the same building, home or location (if not at home) during the meal challenge (and for 4 hours following the start of the meal). They must be able to check SMBG (in case it is needed) and give glucose/administer glucagon if required.

### **Exercise Challenge for all Subjects (during Study Period only):**

The following exercise challenges are required during the study period:

- 2 exercise challenges at setpoint of 120 mg/dL, between Visits 9 and 11 of the study period
- 2 exercise challenges at setpoint of 100 mg/dL, between Visits 12 and 13 of the study period
- 1 exercise challenge at setpoint investigator's discretion, at any time after Visit 13of the study period)

Conditions at start of the exercise challenges:

[figure not shown]
- SG should be present at the start of each exercise challenge
- The investigator or his/her staff will determine the minimum BG for each subject at the start of each exercise challenge. It will be noted on the subject's exercise log

Timing	Settings/Conditions	Exercise duration	Notes
Study Period, between Visits 9 and 11	SmartGuard (120 mg/dL setpoint)	Min 30 minutes, up to 1.5 hours	Challenge must take place on days without meal challenge
Study Period, between Visits 9 and 11	SmartGuard (120 mg/dL setpoint)	Min 30 minutes, up to 1.5 hours	Challenge must take place on days without meal challenge
Study Period, between Visits 12 and 13	SmartGuard (100 mg/dL setpoint)	Min 30 minutes, up to 1.5 hours	Challenge must take place on days without meal challenge
Study Period, between Visits 12 and 13	SmartGuard (100 mg/dL setpoint)	Min 30 minutes, up to 1.5 hours	Challenge must take place on days without meal challenge
Study Period Any time after Visit 13	SmartGuard (Auto Basal target at investigator's discretion)	Min 30 minutes, up to 1.5 hours	Challenge must take place on days without meal challenge

### **Exercise Challenges Details:**

To fulfill the exercise challenge requirement, subjects will be asked to engage in 0.5 up to 1.5 hours of physical exercise. During this time, subjects should use either the Auto Basal setpoint target of 100 mg/dL or 120 mg/dL, depending on what is required at that time of the study period, unless a subject prefers to use the 150 mg/dL temp target before, during and immediately after the exercise challenges. The FoodPrint™ app (as well as questions that will be asked by site staff during visits following exercise challenges) will be used by subjects to collect information about exercise type, date, time (start and finish of exercise) and duration. The timing of the exercise challenge will be at the investigator's discretion. A photograph should be taken on each day of the exercise challenges to indicate where the exercise took

20-DEC-2023 Page 12 of 25 Revision 3.0

place. The subject's parents/caregivers (if applicable) or companion must be physically present in the same building, home or location (if not at home) during the exercise challenge, must be able to check SMBG (in case it is needed) and give glucose/administer glucagon as needed. Examples of types of exercise include, but are not limited to:

- Running
- Cycling
- Swimming
- Hiking
- Walking
- Games (e.g. Wii interactive video games)
- Indoor/outdoor playground (Pediatric subjects)
- Yoga/stretching
- Any sport activity that involves ongoing physical movement (e.g., tennis, golf, basketball, volleyball, soccer)
- Dancing
- Zumba
- Aerobics
- Spinning

### **Companions:**

Subjects will be required to have a companion who resides (or will live) in the same building (or home) during the study at night, and also to be physically present in the same building, home or location (if not at home) during the exercise and meal challenges. A companion should be present during meal challenges and for 4 hours following the start of the meal. Companions should be able to check SMBG, give glucose and/or administer glucagon.

### Safety Considerations with the Use of Lyumjev insulin:

Sites will send out an email to each subject during weeks where no visit is scheduled to inquire about insulin infusion with Lyumiev insulin. The email will ask subjects whether or not they have experienced any insulin infusion reactions with the use of the Lyumjev insulin. The email will also remind subjects that sites should be called if any issues with Lyumjev insulin infusion occur. During such calls, photos and video should be used, if possible.

### 5.1 Duration

The study is anticipated to last approximately 18 months from first investigational center initiation to finalization of all data entry and monitoring procedures for data cleaning. Individual subject participation is expected to be approximately 120 days.

## 5.2 Rationale

Previous clinical investigations have confirmed the safety and clinical performance of the MiniMed 780G insulin pump when used to deliver Humalog or Novolog U100 insulin to patients 7-80 years of age. Insilico modeling indicates that the use of Lyumjev U100 insulin with the MiniMed780G pump will result in

### **CIP335 Statistical Analysis Plan Form** Medtronic 20-DEC-2023 Revision 3.0 Page 13 of 25

similar outcomes. This investigation is intended to provide additional confirmation of the safety of the 780G insulin pump used in combination with Lyumjev U100 insulin in humans.

#### **Determination of Sample Size** 6.

## 6.1 Sample Size and Investigational Centers

A total of up to 250 subjects with insulin-requiring type 1 diabetes age 7-80 will be enrolled at up to 25 investigational centers across the United States in order to have at least 200 subjects enter the study period. Up to 125 subjects will be enrolled in the pediatric age group (7-17 years of age) and up to 125 in the adult age group (18 years or older):

Subject Age Group	ect Age Group Sub-groups	
Pediatric	All Pediatric	Minimum 100 Subjects
Age 7 – 17 years	Age 7 - 13 years	Minimum 20 Subjects
	Age 14 - 17 years	Minimum 20 Subjects
Adult Age 18 - 80 years	N/A	Minimum 100 Subjects

A minimum of 10 subjects and a maximum of 40 subjects is targeted for enrollment at each investigational center to ensure that the results from the individual investigational center may be pooled for analysis.

Investigational centers will be encouraged to enroll a study population that represents a wide variety of backgrounds.

## 6.2 Sample Size Considerations/Sample Size Justification

## 6.2.1 Age 18-80

Sample size for the primary safety endpoint: the overall mean change in Glycosylated hemoglobin (HbA1c) from baseline to end of 3-month study period

The overall mean change in HbA1c from baseline to end of 3-month study period from 670G (CEP294 HCL age 18 to 75, N = 101) study was -0.50%. Assuming the mean change in HbA1c from baseline to end of 3-month study period from 780G is the same as 670G, with a standard deviation of 0.7%, SAS power and sample size calculator with one sample T test shows that a total of 80 subjects will provide > 80% power, to detect that mean HbA1c is less than -0.50% with a margin of 0.4% at a significance level of 0.025 (one-sided).

20-DEC-2023 Page 14 of 25 Revision 3.0

Sample size for the primary effectiveness endpoint: the mean % of time in range (TIR 70-180 mg/dL)

The mean % of time in target from 670G (CEP294 HCL age 18 to 75, N = 104) study was 73.7%. Assuming the mean time in target (%) from 780G is the same as 670G, with a standard deviation of 8.8%, SAS power and sample size calculator with one sample T test shows that a total of 80 subjects will provide > 80% power, to detect that mean % of time in target is greater than 73.7% with a margin of -7.5% at a significance level of 0.025 (one-sided).

Sample size for the secondary effectiveness endpoint: the mean % of time below range (< 54 mg/dL)

The mean % of time below range (< 54 mg/dL) from 670G (CEP294 HCL age 18 to 75, N = 104) study was 0.86%. Assuming the mean time below target (%) from 780G is the same as 670G, with a standard deviation of 0.79%, SAS power and sample size calculator with one sample T test shows that a total of 80 subjects will provide > 80% power, to detect that mean % of time below range is less than 0.86% with a margin of 2% at a significance level of 0.025 (one-sided).

Sample size for the secondary effectiveness endpoint: the mean % of time in range (TIR 70-180 mg/dL)

The mean % of time in target from 670G (CEP294 HCL age 18 to 75, N = 104) study was 73.7%. Assuming the mean time in target (%) from 780G is 76%, with a standard deviation of 7.2%, SAS power and sample size calculator with one sample T test shows that a total of 80 subjects will provide > 80% power, to detect that mean % of time in target is greater than 73.7% at a significance level of 0.025 (one-sided).

### 6.2.2 Age 7-17

[figure not shown]
Sample size for the primary safety endpoint: the overall mean change in HbA1c from baseline to end of 3-month study period

The overall mean change in HbA1c from baseline to end of 3-month study period from 670G (CEP294 and CEP302 HCL age 7 to 17, N = 125) study was -0.38%. Assuming the mean change in HbA1c from baseline to end of 3-month study period from 780G is the same as 670G, with a standard deviation of 0.7%, SAS power and sample size calculator with one sample T test shows that a total of 80 subjects will provide > 80% power, to detect that mean change of HbA1c is less than -0.38% with a margin of 0.4% at a significance level of 0.025 (one-sided).

Sample size for the primary effectiveness endpoint: the mean % of time in range (TIR 70-180) mg/dL)

The mean % of time in target from 670G (CEP294 and CEP302 HCL age 7 to 17, N = 125) study was 65.3%. Assuming the mean time in target (%) from 780G is the same as 670G, with a standard deviation of 8%, SAS power and sample size calculator with one sample T test shows that a total of 80 subjects will provide > 80% power, to detect that mean % of time in target is greater than 65.3% with a margin of -7.5% at a significance level of 0.025 (one-sided).

20-DEC-2023 Page 15 of 25 Revision 3.0

Sample size for the secondary effectiveness endpoint: the mean % of time below range (< 54 mg/dL)

The mean % of time below range (< 54 mg/dL) from 670G (CEP294 and CEP302 HCL age 7 to 17, N = 125) study was 0.71%. Assuming the mean time below target (%) from 780G is the same as 670G, with a standard deviation of 0.60%, SAS power and sample size calculator with one sample T test shows that a total of 80 subjects will provide > 80% power, to detect that mean % of time below range is less than 0.71% with a margin of 2% at a significance level of 0.025 (one-sided).

Sample size for the secondary effectiveness endpoint: the mean % of time in range (TIR 70-180 mg/dL)

The mean % of time in target from 670G (CEP294 and CEP302 HCL age 7 to 17, N = 125) study was 65.3%. Assuming the mean time in target (%) from 780G is 67.6%, with a standard deviation of 7%, SAS power and sample size calculator with one sample T test shows that a total of 80 subjects will provide > 80% power, to detect that mean % of time in target is greater than 65.3% at a significance level of 0.025 (one-sided).

## **6.2.3 Expected Drop-out Rates**

Incorporating the expected drop-out rates, a total of up to 250 subjects will be enrolled, in order to have 200 subjects enter the study period.

#### Statistical Methods 7.

# 7.1 Study Subjects

# 7.1.1 General Aspects of Analysis

All data collected from the time of screening until the end of the study will be collected on eCRFs, subject questionnaires, and electronically by uploading the various devices. Data and analysis will be summarized in a Clinical Study Report. Any deviations from original statistical plan and the rationale will be described in the Clinical Study Report.

#### 7.1.2 **Disposition of Subjects**

The number of subjects enrolled, completed, and early terminated in the study will be presented. The reasons for discontinuing prior to study completion will be summarized.

20-DEC-2023 Revision 3.0

Page 16 of 25

#### 7.1.3 **Clinical Investigation Plan (CIP) Deviations**

All protocol deviations will be presented in the listings.

#### 7.1.4 **Analysis Sets**

### • Intention to Treat (ITT) Population

The ITT population will include all subjects who start the study period. Primary safety, primary effectiveness, secondary effectiveness and descriptive endpoints will be evaluated for ITT population.

### Per Protocol (PP) Population

The PP population will include all subjects who complete the study period, are in Auto Mode ≥ 80% of the time and without any major deviations. Primary safety, primary effectiveness and secondary effectiveness endpoints will be evaluated for PP population as the sensitivity/supplementary analyses.

### Safety Population

The Safety Population will include all enrolled subjects (subjects who signed Informed Consent Form (ICF)). Safety adverse events data summary will be evaluated for safety population.

## 7.2 General Methodology

Summary statistics for continuous variables will be represented by number of subjects (n), mean, median, standard deviation and categorical variables will be represented by counts and percentages. Pvalues for hypothesis testing will be evaluated based on one-sided testing using significance level of 0.025. Confidence intervals if needed will be reported as two-sided 95% confidence intervals. For primary safety, primary effectiveness and secondary effectiveness endpoints, normality will be verified for appropriate statistical methodology. Comparisons between the outcomes in study period and the threshold will be performed using one sample T-test for testing the statistical significance of the difference if normality assumption is met or Wilcoxon signed rank test if normality assumption is not met.

[figure not shown]
The templates for Tables, Listings and Figures (TLFs) will be available in the TLFs document.

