## 7.9.2 Primary Safety Endpoint

### Age 18-80:

The overall mean change in HbA1c,  $\Delta\mu_{780G}$ , from baseline to end of 3-month study period will be estimated and compared to the threshold of -0.50% with a margin of 0.4%. A significance level of 0.025 (one-sided) will be used. Analysis will be performed on the ITT and PP populations.

The hypothesis is mathematically expressed as:

$$H_0$$
:  $\Delta \mu_{780G} \ge -0.50\% + 0.4\%$ 

Ha: 
$$\Delta \mu_{780G} < -0.50\% + 0.4\%$$

The null hypothesis will be tested against the alternative hypothesis using one sample t test if normality assumption is met, Wilcoxon signed rank test if normality assumption is rejected. The mean change in HbA1c from baseline to end of 3-month study period is less than -0.50% with a margin of 0.4% for age 18-80 will be concluded if null hypothesis is rejected.

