### **CIP335 Statistical Analysis Plan Form** Medtronic 20-DEC-2023 Page 20 of 25 Revision 3.0

The null hypothesis will be tested against the alternative hypothesis using one sample t test if normality assumption is met, Wilcoxon signed rank test if normality assumption is rejected. The mean change in HbA1c from baseline to end of 3-month study period is less than -0.38% with a margin of 0.4% for age 7-17 will be concluded if null hypothesis is rejected.

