## 7.9.3.1 Primary Effectiveness Endpoint

### Age 18-80:

The mean % of time, µ780G, in range (TIR 70-180 mg/dL) will be estimated and compared to the threshold of 73.7% with a margin of -7.5%. A significance level of 0.025 (one-sided) will be used. The 7.5%, which is approximately 100 minutes increase in TIR per day, was also observed from the HCL pivotal trials. Analysis will be performed on the ITT and PP populations.

The hypothesis is mathematically expressed as:

H0:  $\mu_{780G} \le 73.7\% - 7.5\%$ 

 $H_a$ :  $\mu_{780G} > 73.7\% - 7.5\%$ 

The null hypothesis will be tested against the alternative hypothesis using one sample t test if normality assumption is met, Wilcoxon signed rank test if normality assumption is rejected. Mean % of time in target from MiniMed 780G system utilizing Lyumjev insulin is greater than 73.7% with a margin of -7.5% for age 18-80 will be concluded if null hypothesis is rejected.

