## 7.9.3.2 Analysis of Secondary Effectiveness Endpoints

### Age 18-80:

• Secondary Effectiveness Endpoint: The mean % time,  $\mu_{780G}$ , in hypoglycemia (< 54 mg/dL) will be estimated and compared to the threshold of 0.86% with a margin of 2%. A significance level of 0.025 (one-sided) will be used. Analysis will be performed on the ITT and PP populations.

The hypothesis is mathematically expressed as:

 $H_0$ :  $\mu_{780G} \ge 0.86\% + 2\%$ 

 $H_a$ :  $\mu_{780G} < 0.86\% + 2\%$ 

The null hypothesis will be tested against the alternative hypothesis using one sample t test if normality assumption is met, Wilcoxon signed rank test if normality assumption is rejected. Mean % of time below range from MiniMed 780G system utilizing Lyumjev insulin is less than 0.86% with a margin of 2% for age 18-80 will be concluded if null hypothesis is rejected.

• Secondary Effectiveness Endpoint: The mean % of time,  $\mu_{780G}$ , in range (TIR 70-180 mg/dL) will be estimated and compared with a significance level of 0.025 (one-sided). Analysis will be performed on the ITT and PP populations.

[figure not shown]
The hypothesis is mathematically expressed as:

H0:  $\mu_{780G}$  ≤73.7%

 $H_a$ :  $\mu_{780G} > 73.7\%$ 

The null hypothesis will be tested against the alternative hypothesis using one sample t test if normality assumption is met, Wilcoxon signed rank test if normality assumption is rejected. Mean % of time in target from MiniMed 780G system utilizing Lyumjev insulin is greater than 73.7% for age 18-80 will be concluded if null hypothesis is rejected.

20-DEC-2023 Page 22 of 25 Revision 3.0

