### Age 7-17:

Secondary Effectiveness Endpoint: The mean % time, µ780G, in hypoglycemia (< 54 mg/dL) will be estimated and compared to the threshold of 0.71% with a margin of 2%. A significance level of 0.025 (one-sided) will be used. Analysis will be performed on the ITT and PP populations.

The hypothesis is mathematically expressed as:

H0:  $\mu_{780G} \ge 0.71\% + 2\%$ 

 $H_a$ :  $\mu_{780G} < 0.71\% + 2\%$ 

The null hypothesis will be tested against the alternative hypothesis using one sample t test if normality assumption is met, Wilcoxon signed rank test if normality assumption is rejected. Mean % of time below range from MiniMed 780G system utilizing Lyumjev insulin is less than 0.71% with a margin of 2% for age 7-17 will be concluded if null hypothesis is rejected.

 Secondary Effectiveness Endpoint: The mean % of time, μ780G, in range (TIR 70-180 mg/dL) will be estimated and compared with a significance level of 0.025 (one-sided). Analysis will be performed on the ITT and PP populations.

The hypothesis is mathematically expressed as:

H0:  $\mu_{780G}$  ≤65.3%

 $H_a$ :  $\mu_{780G} > 65.3\%$ 

[figure not shown]
The null hypothesis will be tested against the alternative hypothesis using one sample t test if normality assumption is met, Wilcoxon signed rank test if normality assumption is rejected. Mean % of time in target from MiniMed 780G system utilizing Lyumjev insulin is greater than 65.3% for age 7-17 will be concluded if null hypothesis is rejected.

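### All eight confirmatory claims are about means, but an unspecified normality check can switch the test to the Wilcoxon signed rank test, which does not test a mean under skew

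*SAP*

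**What the plan says.** SAP 7.2 states for the primary and secondary endpoints that "normality will be verified for appropriate statistical methodology", and then chooses between a one-sample t-test and the "Wilcoxon signed rank test if normality assumption is not met". SAP 7.9.2, 7.9.3.1 and 7.9.3.2 repeat the switch for every hypothesis (for example "Wilcoxon signed rank test if normality assumption is rejected" for HbA1c in ages 7–17). Neither the SAP nor the protocol names a normality test, a level or a graphical rule.

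There are eight hypotheses, four per age group: HbA1c change, time in range (TIR) with a margin, time below 54 mg/dL, and TIR superiority. Each is written on a mean. So is each conclusion, whichever test rejected: in adults, "Mean % of time in target from MiniMed 780G system utilizing Lyumjev insulin is greater than 73.7% for age 18-80 will be concluded"; in children and adolescents, "Mean % of time in target from MiniMed 780G system utilizing Lyumjev insulin is greater than 65.3% for age 7-17 will be concluded". No alternative wording is given for the Wilcoxon branch.

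On estimation, SAP 7.2 says "Confidence intervals if needed will be reported as two-sided 95% confidence intervals". The sample size sections (SAP 6.2, Protocol 14.5) rest on the one-sample t-test only.

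**The concern.** The signed rank test is a test of the pseudomedian. That equals the mean when the distribution is symmetric, but skew is a common reason for a normality check to fail. The plan therefore moves to Wilcoxon in circumstances where Wilcoxon may no longer address the stated hypothesis, and still words the result as a mean. The benchmarks are themselves means from the earlier 670G studies, so a pseudomedian is not the matching quantity.

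Three things follow.

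- With the true mean exactly at the null limit, the rejection rate can lie above or below 2.5%, depending on the direction of skew.
- The confirmatory test is not fully determined before the data are seen, because the check that selects it is not defined.
- A Wilcoxon p-value may be reported without an interval for the mean it is said to support.

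A smaller gap: SAP 7.4 combines five imputations of HbA1c into one inference but gives no rule for pooling Wilcoxon results. This matters only if end-of-study HbA1c is missing and normality also fails.

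**Working it through.** **Inputs (SAP 6.2, 7.9; Protocol 14.5).** One-sided level 0.025; 80 subjects per age group in the power statements.

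| Endpoint | Age group | Null limit | Planning mean | SD |
|---|---|---|---|---|
| HbA1c change | 18–80 | −0.50 + 0.4 = −0.10% | −0.50% | 0.7% |
| HbA1c change | 7–17 | −0.38 + 0.4 = +0.02% | −0.38% | 0.7% |
| TIR with margin | 18–80 | 73.7 − 7.5 = 66.2% | 73.7% | 8.8% |
| TIR with margin | 7–17 | 65.3 − 7.5 = 57.8% | 65.3% | 8% |
| Time <54 | 18–80 | 0.86 + 2 = 2.86% | 0.86% | 0.79% |
| Time <54 | 7–17 | 0.71 + 2 = 2.71% | 0.71% | 0.60% |
| TIR superiority | 18–80 | 73.7% | 76% | 7.2% |
| TIR superiority | 7–17 | 65.3% | 67.6% (SAP), 67.5% (protocol) | 7% |

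**Step 1: the plan's power figure.** Power comes from the noncentral t with 79 df and noncentrality (distance to limit / SD) × √80.

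- HbA1c: (0.4/0.7) × 8.944 = 5.11, power 99.9%.
- TIR with margin: (7.5/8.8) × 8.944 = 7.62 and (7.5/8) × 8.944 = 8.39, power above 99.99%.
- Time <54: (2/0.79) × 8.944 = 22.6 and (2/0.60) × 8.944 = 29.8, power above 99.9%.
- TIR superiority, adults: (2.3/7.2) × 8.944 = 2.86, power 80.6%.
- TIR superiority, ages 7–17: (2.3/7) × 8.944 = 2.94, power 82.7%; with the protocol's mean, (2.2/7) × 8.944 = 2.81, power 79.3%.

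The stated power of more than 80% is reproduced, except that the protocol's 67.5% falls just short. At n=100 the three superiority figures are 88.6%, 90.2% and 87.5%.

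**Step 2: is the switch realistic?** Time <54 cannot be negative. A normal curve with the planning values would put Φ(−0.86/0.79) = 13.8% of adults and Φ(−0.71/0.60) = 11.8% of ages 7–17 below zero. With gamma data at those values, Shapiro-Wilk at 0.05 rejected in every simulated trial, and the adult pseudomedian is about 0.74% against a mean of 0.86%.

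**Step 3: error for the mean with the true mean at the limit.** 50,000 simulated trials per scenario, n=80 and 100; simulation standard error near 2.5% is √(0.025 × 0.975 / 50,000) ≈ 0.07 percentage points. The documents give neither the normality test nor the shapes. Assumed: Shapiro-Wilk at 0.05, beta for TIR, gamma for time <54, a symmetric shape for HbA1c, all with the plan's SDs.

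| Endpoint | Age group | Switching rule | t-test |
|---|---|---|---|
| TIR superiority | 18–80 | 3.7–3.9% | 2.8% |
| TIR superiority | 7–17 | 2.9–3.0% | 2.6–2.7% |
| TIR with margin | 18–80 | 3.3–3.4% | 2.7–2.8% |
| TIR with margin | 7–17 | 2.7–2.8% | 2.5–2.6% |
| Time <54 | 18–80 | 5.2–6.1% | 3.0–3.2% |
| Time <54 | 7–17 | 4.2–4.7% | 2.8–3.0% |
| HbA1c | both | 2.4–2.5% | 2.4–2.5% |

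The implied skew at the superiority limit is only −0.34 (adults) and −0.19 (ages 7–17). For time <54 the gamma skew at the limit is 2 × SD/mean: 2 × 0.79/2.86 = 0.55 and 2 × 0.60/2.71 = 0.44.

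**Step 4: stress cases, not expected values.** For TIR or HbA1c, skew of magnitude 1 toward poor outcomes gives 10.8–13.0% against 3.4–3.6% for the t-test; the opposite skew gives 0.3–0.6% against 1.7–1.8%. If the planning ratio of SD to mean for time <54 also held at the limit, the rule would give 28–33% in adults and 24–29% in ages 7–17, against 4.2–4.5%.

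**Step 5: how often would the decision change at the design means?** The rule and the t-test disagree in 0% of trials for TIR with margin and for time <54, in 0–0.3% for HbA1c (skew −1 to +1), and for TIR superiority with beta data in 2.0–2.2% (adults) and 0.5–0.8% (ages 7–17).

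**The case against.** The strongest reply is about weight. Cohort success rests only on the two primary endpoints (SAP 7.9.1), and at the planning values their decisions are almost unaffected by the choice of test. Time <54 would switch nearly always, yet its decision does not change either. What remains is TIR superiority, a secondary endpoint tested last, so an error there passes to no later test. At least 200 subjects are to enter the study period, so n=100 per age group is nearer the plan than n=80. The large error rates need shapes that the documents do not give, and the direction of skew is unknown. The fallback is pre-specified and applied uniformly, and the mean, median and SD are reported in any case. Nor is the t-test exactly nominal under skew.

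All of this stands as a limit on size. It does not remove the mismatch between test and conclusion.

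A narrower repair is possible: name the normality criterion, word the Wilcoxon result as a location statement, and always give an interval for the mean. It would cure most of the wording problem, but the data would still choose the parameter, and that parameter would be compared with a benchmark that is a mean.

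Timing also deserves care. SAP 3.0 is dated 20 December 2023, and the documents do not say which data had been seen by then, so a change to the confirmatory test should be justified in the record.

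**Conclusion.** The concern holds. As written, the rule can lead to a conclusion about a mean from a test that does not establish it, and the check that triggers the switch is undefined. The effect on cohort success is close to nil unless a true mean lies near its limit. For adult TIR superiority the excess error over the t-test is about one percentage point under bounded shapes with the plan's SDs, and about 0.3 points in ages 7–17. It grows to several points if TIR has a marked tail of low values and reverses if the tail is on the other side. These sizes depend on the assumed Shapiro-Wilk test at 0.05 and the assumed shapes; the mismatch itself does not. It should be fixed because the correction is simple and matches the plan's own hypotheses and power basis.

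**What to change.** In SAP 7.2, 7.9.2 and 7.9.3, replace the switch with wording such as:

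> Each primary and secondary endpoint will be tested with a one-sample t-test on the mean at one-sided 0.025 and always reported with its two-sided 95% confidence interval. This is the sole confirmatory test. No normality pre-test will be used to choose the test.

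In SAP 7.4, state that the HbA1c mean and standard error are estimated within each imputation and pooled by Rubin's rules. Report a bootstrap interval for the mean and the Wilcoxon test as supplementary analyses that cannot decide success.

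**Cost.** SAP wording only; the planned t-test power is unchanged. Relative to the switching rule, simulated rejection rates for adult TIR superiority at n=80 change as follows:

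- beta data: 82.1% to 79.9%
- skew −0.5: 83.3% to 79.2%
- skew −1: 90.8% to 78.3%
- skew +0.5: 75.8% to 82.1%

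In ages 7–17 with beta data they change from 82.5% to 81.8% (mean 67.6%) or from 79.5% to 78.8% (mean 67.5%), and fall by 11–13 points at skew −1. Part of the loss at negative skew is the removal of rejections that are not valid for the mean. The t-test keeps some excess error for skewed time <54: about 3% at the stated SDs, and up to about 4.5% in the stress case.
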